5.3.4 Liver Function Tests

Liver function tests have additional analysis views for this study in accordance with current regulatory guidance. To explore the potential for drug-induced liver injury consistent with *Guidance for Industry “Drug-induced liver injury: premarketing clinical evaluation”* (CDER, CBER, July 2009), subjects will be summarized and listed who meet the following criteria:

- (1) Elevations in either AST or ALT of at least 3-times the upper limit of normal, and

- (2) An accompanying abnormal bilirubin of at least 2-times the upper limit of normal.

5.3.5 Electrocardiography

The heart rate, QT, PR, and QRS intervals will be recorded at each assessment time. No formal inferential statistics will be applied to the ECG data.

For each post-Baseline assessment, descriptive statistics are provided for the assessment value and the change from Baseline to the assessment with mean, median, standard deviation, minimum, and maximum at each assessment time.

In addition, the number of subjects with corrected and uncorrected QT values >500 msec will be summarized. Values from individual tracings within the triplicate measurement on Day 1, time 0 hour that are >500 msec will not be included in the categorical analysis unless the average from that triplicate measurement is also >500 msec.

Electrocardiography data will be summarized by Baseline and Change from Baseline to each scheduled assessment time with descriptive statistics.

Corrections to QT intervals will be made by Fridericia's method (QTcF). Categorical analysis will be done consistent with ICH E14, "Clinical evaluation of QT/QTc interval prolongation and proarrhythmic potential for non-antiarrhythmic drugs" (October 2005).

In accordance with ICH E14, subjects will be categorized and summarized as described above according to:

- Absolute QTc interval prolongation:
 - QTc interval > 450
 - QTc interval > 480
 - QTc interval > 500
- Change from Baseline in QTc interval:
 - QTc interval increases from Baseline > 30
 - QTc interval increases from Baseline > 60.

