4.2 EXCLUSION CRITERIA

Participants presenting with any of the following will be excluded from participation in the study.

1. The subject is felt by the investigator to be unsuitable (on the basis of health, compliance, caregiver availability, or for any other reason) for inclusion in the study.
2. Subjects with serious suicide risk. If there are “yes” answers on items 4, 5 or on any behavioral question of the C-SSRS, a suicide risk assessment must be done by a qualified mental health professional with expertise in the evaluation of suicidality in the elderly (e.g., psychiatrist, geriatrician or neurologist specializing in treatment of patients with AD) to determine whether it is safe for the subject to participate in the study.
3. Subjects demonstrating a QTcF > 480 msec or a >45 msec increase from the TTP488-301 Baseline value based on the locally read ECG performed at the TTP488-301 Month 18 Visit (TTP488-303 Baseline). Participants with known history of bundle branch block (either right or left) are allowed if absolute QTcF value does not exceed 500 msec. Participants with a functioning pacemaker, indicated by an ECG displaying paced rhythm, are allowed with no QTc upper limit.
4. Other acute or chronic medical or psychiatric condition or laboratory abnormality that may increase the risk associated with study participation or investigational product administration or may prevent the subject from completing the 2-year study or may interfere with the interpretation of study results and, in the judgment of the investigator, would make the subject inappropriate for entry into this trial.

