9.3 SAFETY ANALYSIS

A treatment-emergent adverse event (TEAE) is defined as an AE that was not present at baseline, or an exacerbation of a pre-existing AE. For laboratory data, a treatment-emergent abnormal laboratory value (TEAV) represents an abnormal value that was normal at baseline.

Safety variables of analysis include the following:

- Proportions of patients with any TEAEs
- Proportions of patients with serious TEAEs
- Proportions of patients with severe TEAE
- Proportions of patients with TEAEs leading to study drug discontinuation
- Proportions of patients with TEAEs leading to study withdrawal
- Proportions of patients with drug-related TEAEs
- Proportions of patients with TEAVs
- Proportions of patients meeting DILI criteria
- Proportions of patients meeting ICH E14 criteria for threshold values or threshold changes
- Mean changes from baseline in vital signs
- Mean changes from baseline in clinical laboratory measures
- Mean change from baseline in measures from electrocardiography

Continuous data will be summarized by treatment group using descriptive statistics (number, mean, median, standard deviation, first and third quartiles, minimum, and maximum). Categorical data will be summarized by treatment group using frequency tables (frequencies and percentages).

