Total bilirubin	>2.5 x ULN (>2.7 mg/dL)
AST	>3 x ULN (>102 U/L)
ALT	>3 x ULN (>123 U/L)
Alk Phosphatase	>3 x ULN (>348 U/L)
Creatinine	>2 mg/dL
BUN	>1.4 x ULN (30.8 mg/dL)
Glucose	≤70 mg/dL or ≥270 mg/dL
Uric acid	>12 mg/dL
Sodium	<125 mmol/L or >155mmol/L
Potassium	<3.0 mmol/L or >6.0 mmol/L
Bicarbonate	<16 mmol/L
Calcium	<6.0 mg/dL and >13.0 mg/dL
Triglycerides	>750 mg/dL
Electrocardiogram	
Heart Rate	<50 bpm and ≥/=25% decrease from baseline >100 bpm and ≥/=25% increase from baseline
PR interval	≥200 msec and ≥25% increase from baseline
QRS interval	≥200 msec and ≥25% increase from baseline
QTc interval	≥500 msec ≥30-60 msec increase >60 msec increase
Vitals (sitting)	
SBP	≥190 mmHg (entry is <180 mmHg) Systolic <80 mm Hg Decrease from baseline ≥30 mmHg
DBP	≥120 mmHg (entry is <105) <50 mm Hg

Parameters not provided with specific thresholds for clinical concern: RBC count, eosinophils, basophils, monocytes, direct or indirect bilirubin (just total as shown above), chloride, albumin, total protein, insulin, total cholesterol, HDL, LDL, urinalysis, pulse rate from VS (rely on ECG heart rate).

11 References

- Berg, L. Clinical Dementia rating (CDR). *Psychopharmacol Bull.* 1988;24:637-9.
- Little, RJA, and Rubin, DB. (1987). *Statistical analysis with missing data.* New York: John Wiley and Sons.
- Rubin, D.B. (1976, December). Inference and Missing data. *Biometrika*, Volume 63, Issue 3 (Dec., 1976), 581-592.
- ICH. (1996, July 30). ICH Harmonized tripartite guideline: Structure and content of clinical study reports (E3). International Conference on Harmonization of Technical Requirements for Registration of Pharmaceuticals for Human Use.
- ICH. (1997, July 17). ICH Harmonized tripartite guideline: General considerations for clinical trials (E8). International Conference on Harmonization of Technical Requirements for Registration of Pharmaceuticals for Human Use.
- ICH. (1998, February 5). ICH Harmonized tripartite guideline: Statistical principles for clinical trials (E9). International Conference on Harmonization of Technical Requirements for Registration of Pharmaceuticals for Human Use.

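### The absolute QTc counts in SAP 5.3.5 ignore the baseline value although entry admits subjects already above the thresholds, so new and pre-existing values cannot be told apart; add incident counts and a shift table against both baselines

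*SAP*

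**What the plan says.** ECG is one of the primary endpoints (Protocol 2.2). Protocol 9.3 lists among the safety variables "Proportions of patients meeting ICH E14 criteria for threshold values or threshold changes".

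SAP 5.3.5 implements this in three ways:
- For any QT or QTcF above 500, "the number of subjects with corrected and uncorrected QT values >500 msec will be summarized".
- "In accordance with ICH E14, subjects will be categorized and summarized as described above according to" absolute QTc of >450, >480 and >500.
- The same list has change categories: "QTc interval increases from Baseline > 30", and likewise >60. Change from baseline is also summarized at each visit.

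The absolute counts carry no condition on the baseline value, and no shift table is planned. The only sentence about pre-dose values drops a single Day 1, time 0 tracing above 500 "unless the average from that triplicate measurement is also >500 msec". A high pre-dose average can therefore enter the categorical analysis. The protocol describes no triplicate ECG.

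On entry, criterion 3 of Protocol 4.2 excludes "Subjects demonstrating a QTcF > 480 msec or a >45 msec increase from the TTP488-301 Baseline value". It then allows known bundle branch block up to 500 msec, and "Participants with a functioning pacemaker, indicated by an ECG displaying paced rhythm, are allowed with no QTc upper limit". Protocol 7.1.2 gives the same two exceptions, then restates the 480 limit without them; those statements must be reconciled. The working below follows 4.2.

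SAP 6.1 defines two baselines, one before double-blind drug and one before open-label drug, and assigns the second to safety.

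**The concern.** A subject who enters above a threshold and stays there is counted under a heading that calls the finding prolongation, although nothing has changed. Every subject receives azeliragon, and both displayed groups (prior azeliragon, prior placebo) are on drug, so no concurrent unexposed group shows the background rate. A reader given the proportion above 450 cannot tell how much of it is new.

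The SAP handles comparable safety data differently. Laboratory treatment-emergent abnormal values are limited to subjects normal before dosing (SAP 4.2.4 and 5.3.3). In SAP Section 10, the absolute limits for heart rate, PR and QRS each require a change of at least 25% from baseline as well; the QTc limit of 500 stands alone.

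Blood pressure has a smaller version of the gap. SAP 4.2.3 asks for treatment-emergent values, but 5.3.2 does not repeat the condition. Section 10 annotates its limits with entry values, as in "≥190 mmHg (entry is <180 mmHg", and similarly <105 for diastolic pressure. TTP488-303 has no blood-pressure entry criterion in Protocol 4.1 or 4.2.

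**Working it through.** The plan gives no QTc rate for this analysis, so there is no figure to reproduce.

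**1. Entry limits against count thresholds** (Protocol 4.2 against SAP 5.3.5)

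| Count | Who can already be above it at entry |
|---|---|
| QTcF >450 | any subject above 450 and up to 480; bundle branch block up to 500; paced rhythm |
| QTcF >480 | bundle branch block above 480 and up to 500; paced rhythm |
| QTcF >500 | paced rhythm only |
| Uncorrected QT >500 | no entry limit on this measure |

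**2. Uncorrected QT.** Inverting Fridericia, QT = QTcF × (60/HR)^(1/3), so QT exceeds 500 when HR < 60 × (QTcF/500)³.
- QTcF 480: 60 × 0.96³ = 53.1 bpm. At 50 bpm, QT = 480 × 1.2^(1/3) = 510 msec.
- QTcF 500 (bundle branch block): below 60 bpm.
- QTcF 450: 60 × 0.9³ = 43.7 bpm.

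A slow heart rate can therefore put an ordinary eligible subject above 500 before the first open-label dose.

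**3. What the planned displays can distinguish.** Three hypothetical eligible subjects (QTcF, msec):

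| | TTP488-301 baseline | TTP488-303 baseline | Worst later | Counted >450 | Counted >30 rise | Newly >450 from 303 baseline | Newly >450 from 301 baseline |
|---|---|---|---|---|---|---|---|
| A, unchanged | 465 | 465 | 465 | yes | no | no | no |
| B, rises in this study | 440 | 440 | 465 | yes | no (25) | yes | yes |
| C, continuing azeliragon, rose in TTP488-301 | 410 | 455 | 455 | yes | no (0) | no | yes |

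C is eligible because 455 − 410 = 45, which is not above 45. The planned categories give A, B and C the same result. Incident counts against both baselines separate all three.

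**4. Illustrative size, no drug effect, every input assumed.** Let b be the share above a threshold at baseline, s the share of those above it later, and i the share newly above it among the rest. The unrestricted count is b·s + (1 − b)·i. Take b 2–20%, s 70–90%, i 2–5%.
- Lowest count: 0.02 × 0.7 + 0.98 × 0.02 = 3.4%. Highest: 0.20 × 0.9 + 0.80 × 0.05 = 22.0%.
- The incident proportion among those at risk is i itself, 2–5%.
- Lowest pre-existing share: 0.014/(0.014 + 0.98 × 0.05) = 22%. Highest: 0.18/(0.18 + 0.80 × 0.02) = 92%.
- At b = 10%, s = 90%, i = 2%: 0.09 + 0.018 = 10.8%, of which 0.09/0.108 = 83% is pre-existing.

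A simulation of non-paced subjects with no drug effect gives a second view of >450. It assumed mean QTcF 415–425, between-subject SD 18, within-subject SD 8–12 and four post-baseline ECGs. It applied the 480 limit but not the 45 msec rule. Between 7.6% and 25.8% had a value above 450, and 29–46% of those were already above it at baseline. Among subjects at or below 450 at baseline, 4.9–18.6% exceeded it later from visit noise alone.

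**The case against.** The strongest objection is to the obvious remedy. A reader might infer that the absolute counts should be restricted to subjects below the threshold at the TTP488-303 baseline. For subjects continuing on azeliragon that baseline follows 18 months of double-blind treatment, so the restriction would remove subject C, whose QTc lengthened on drug and stayed long. In a study whose primary objective is long-term safety, that is the wrong loss. This stands: incident counts should be added, not substituted, and should use both baselines.

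The SAP also plans >30 and >60 msec increases, change from baseline at each visit, and a listing of QTc data meeting ICH E14 criteria (SAP Section 9). A subject paced at 510 throughout would enter neither increase category. This is real mitigation, and the plan cannot be said to lack baseline-adjusted QTc analysis. It still leaves A, B and C alike in the categorical summary, and a listing does not correct a summary proportion.

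The absolute categories are descriptive, tied to ICH E14 and not labelled treatment-emergent. That is fair, and is why the planned counts should stay.

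Protocol 9.0 places the key analysis in a separate integrated plan. That plan is not in these documents, and this SAP still reports the study alone.

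Two further points stand. The protocol's recorded ECG interpretation is only normal or abnormal with or without clinical significance (7.1.2), so pacing or block status may not be in the database. And for blood pressure, SAP 4.2.3 already supplies the treatment-emergent term; the fault is that 5.3.2 and Section 10 do not carry it through.

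**Conclusion.** The concern holds in a limited form. As written, the absolute QT/QTc counts mix values present at entry with values that arise later. This follows from the text without any assumption about the data. The reach differs by threshold: broad at >450, narrow at >480, paced subjects only for QTcF >500, and heart-rate dependent for uncorrected QT.

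The size is not known. The documents give no baseline QTc distribution and no frequency of pacing or block. The 22–92% range shows only how strongly the answer depends on those inputs. A reader might infer that most of the reported counts will be false signals; the documents do not support that. Nor would an incident count be a drug-effect rate, since visit noise alone produces new exceedances.

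Because ECG is a primary endpoint and the remedy is cheap, the change should be made before database lock. It affects how the safety result can be read, not the conduct of the study.

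**What to change.** In SAP 5.3.5:
- Keep the planned absolute counts, for post-baseline values only. Remove the Day 1 triplicate sentence or reconcile it with the protocol.
- Add incident counts for each threshold, including uncorrected QT >500, with subjects at or below that threshold at baseline as denominator.
- Add a table of baseline category by worst post-baseline category.
- Show both by TTP488-301 treatment group. For subjects continuing on azeliragon, show them also against the pre-double-blind baseline. SAP 6.1 already defines it; its safety sentence needs a matching exception.
- Identify paced and bundle-branch-block subjects separately where that status is recorded.

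In SAP 5.3.2, state that the treatment-emergent condition of 4.2.3 applies to the absolute blood-pressure limits of Section 10. Delete the entry notes there, which match no TTP488-303 criterion.

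The cost is SAP wording and one extra table. No new measurement is needed: exclusion criterion 3 already requires both the Month 18 QTcF and the TTP488-301 Baseline value. Only the pacing and block split may be incomplete, which is why it is conditional.

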5.4 Pharmacokinetics Analysis

5.4.1 Methodology for PK Analysis

Data resulting from blood sampling for trough concentrations of azeliragon and its metabolites TTP1494, TTP2266, and TTP2123 will be collected and analyzed using descriptive statistical methods.

No formal inferential statistics will be applied to the pharmacokinetic data. Potential relationships between azeliragon concentrations and treatment effects may be examined.

5.5 Exploratory Analysis

The analyses described in this analysis plan are intended to be done. It is noted that additional analyses may be done for this study. These additional analyses may or may not be reported.

5.6 Concomitant Medications

Concomitant medications will be summarized by drug category and listed.

6 Data Conventions

The following analysis conventions will be used in the statistical analysis.

6.1 Definition of Baseline

Two baselines will be used in this study: (1) the latest assessment prior to the first dose of double-blind study drug, and (2) the latest assessment prior to the first dose of open-label study drug. For safety evaluations, the Baseline assessment for all measurements will be the latest available, valid measurement taken prior to the initiation of study medication in TTP488-303.

6.2 Missing Data

In general, missing clinical data will not be imputed, except where explicitly defined. In the event of study withdrawal, a subject's final assessment will be used as the endpoint value, if applicable. For Trail Making Test A & B, if the assessment was not done due to cognitive reasons, the max score would be imputed. Note that the reason for "not-done" assessment is captured in the eCRF, and the specify field provides reason why. If the reason relates to cognitive reasons, the maximum time for Trails A (150 seconds) or for Trails B (300 seconds) is used.

Data are considered to be "on-treatment" if the assessment or collection follows the first administration of study medication and if the assessment occurs within 45 days following the final administration of study medication, justified based on the long half-life of this drug.

Dates with missing fields will not have days imputed.

6.3 Dropouts

If a subject withdraws from the study, if the date of an adverse event is not available and a determination of whether or not the event is treatment emergent cannot be made, by convention the event will be considered to be treatment emergent.

6.4 Visit Windows

Assessments taken outside of protocol allowable windows will be displayed according to the case report form (CRF) assessment recorded by the investigator.

6.5 Unscheduled Assessments

Extra assessments (laboratory data or vital signs associated with non-protocol clinical visits or obtained in the course of investigating or managing adverse events) will be included in listings, but not summaries. If more than one laboratory value is available for a given visit, the

observation identified by the investigator to be the scheduled assessment will be used in summaries; all observations will be presented in listings.

Data from unscheduled assessments will be included in longitudinal data summaries (e.g., minimum, maximum over time). Data planned at scheduled times for which unscheduled assessments are taken will not be reflected in by-visit summaries.

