4.2.4 Clinical laboratory assessments

Routine clinical laboratory data will be summarized with descriptive statistics on assessment values and change from Baseline. Routine clinical laboratory data will also be evaluated on the basis of laboratory-defined reference ranges and clinically important values or changes, as defined in this document (Section 10). Routinely collected laboratory safety data that are not required by the protocol will be considered source data, and will not be captured for inclusion into the study database. In TTP488-303, the clinical laboratory blood samples will be collected at Months 6, 12, 18 and 24 or in the event of early termination.

Definition:

- A treatment-emergent abnormal value (TEAV) is a laboratory value that is abnormal after administration of study medication that was normal prior to study medication administration.
- A TEAV of potential clinical concern is a value or change that meets criteria specified in this SAP in Section 10.

Laboratory analytes in this study include:

- Hematology
 - Hemoglobin
 - Hematocrit
 - Erythrocyte (RBC) count
 - Platelet count
 - Total leukocyte (WBC) count
 - MCV
 - Leukocyte differential (percent and total)
 - Total neutrophils
 - Eosinophils
 - Monocytes
 - Basophils
 - Lymphocytes
- Clinical chemistry
 - BUN
 - Creatinine
 - Glucose
 - HbA1c
 - Calcium
 - Sodium
 - Potassium
 - Chloride
 - Bicarbonate
 - AST
 - ALT
 - GGT
 - LDH
 - Total bilirubin
 - Alkaline phosphatase
 - Uric acid
 - Albumin
 - Total protein

Safety variables of analysis include:

- Subjects with TEAVs
- Subjects with TEAVs of potential clinical concern (based on criteria in this SAP)
- Subjects with a TEAV in a liver function test (LFT)

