5.3.2 Vital Signs

Subjects with vital signs meeting the criteria in Section 10 of this SAP for values of potential clinical concern will be flagged and summarized. Proportions of subjects with vital signs of potential clinical concern will be examined for the treatment groups.

No formal inferential statistics will be applied to the vital signs data.

For each post-Baseline assessment, descriptive statistics are provided for the assessment value and the change from Baseline to the assessment with mean, median, standard deviation, minimum, and maximum at each assessment time.

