5.3.3 Routine Clinical Laboratory Measurements

Because “exacerbations” of pre-existing abnormalities in laboratory analytes are examined using clinical judgment and are reported as TEAEs, additional analysis on TEAVs is limited to subjects with values that are normal prior to dosing and abnormal after dosing. Potentially clinically significant abnormalities in laboratory analytes are to be reported as TEAEs and summarized as clinical TEAEs.

Subjects with clinical laboratory data meeting the criteria in Section 10 of this SAP for values of potential clinical concern will be flagged and summarized. Proportions of subjects with clinical laboratory values of potential clinical concern will be examined for the treatment groups.

For each post-Baseline assessment, descriptive statistics are provided for the assessment value and the change from Baseline to the assessment with mean, median, standard deviation, minimum, and maximum at each assessment time.

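### SAP 6.5 contradicts itself on off-schedule laboratory and vital-sign values, and no section says which rule governs the TEAV, Section 10 and DILI counts

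*SAP*

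**What the plan says.** SAP 6.5 has two paragraphs on off-schedule data.

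- **First paragraph.** Extra laboratory and vital-sign values come from non-protocol visits or are "obtained in the course of investigating or managing adverse events) will be included in listings, but not summaries". There is no by-visit qualifier. A second rule begins "If more than one laboratory value is available for a given visit": the value that the investigator marks as the scheduled one goes into summaries, and all values are listed.
- **Second paragraph.** "Data from unscheduled assessments will be included in longitudinal data summaries (e.g., minimum, maximum over time"), and then "Data planned at scheduled times for which unscheduled assessments are taken will not be reflected in by-visit summaries".

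The section does not distinguish extra from unscheduled values.

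The subject-level safety counts are defined elsewhere in the SAP:

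- **TEAV (4.2.4):** it "is a laboratory value that is abnormal after administration of study medication" and was normal before dosing.
- **Section 10 vital signs (5.3.2):** "Subjects with vital signs meeting the criteria in Section 10 of this SAP for values of potential clinical concern will be flagged and summarized".
- **Section 10 laboratory values (5.3.3):** subjects meeting the criteria "for values of potential clinical concern will be flagged and summarized".
- **DILI (5.3.4):** "subjects will be summarized and listed who meet the following criteria", namely AST or ALT at least 3 x ULN with bilirubin at least 2 x ULN.

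SAP 9 places the TEAV and potential-concern results inside the laboratory summary, and the vital-sign criteria inside the vital-sign summary. Protocol 9.3 lists the proportions with TEAVs and with DILI criteria among the safety variables. Protocol Section 9 gives no rule for unscheduled values.

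**The concern.** Safety is the primary objective, and these counts are among its main tabulated results. Two programmers following SAP 6.5 could produce different numerators from the same data. SAP 7 requires all summary information to follow the plan and deviations to be documented, so each programmer could call the other's table a deviation. The two readings are not neutral. The literal first sentence can only lower a numerator, and it removes samples that were taken because an adverse event was being investigated.

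**Working it through.** The plan gives no figure to reproduce. The check is a comparison of the text, with some simple arithmetic.

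**1. Which rule applies to the counts?** SAP 5.3.2, 5.3.3, 5.3.4 and 9 call them summarized results or summaries, so the first sentence of 6.5, read literally, excludes off-schedule values from them. A count of subjects who ever met a criterion behaves like a maximum or minimum over time, so the second paragraph would include those values. No passage chooses between the two.

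**2. Who is affected?** Scheduled chemistry is at Months 6, 12, 18 and 24 (SAP 4.2.4), which are Days 180, 360, 540 and 720 in the schedule. Draws are 360 - 180 = 180 days apart, or up to 180 + 14 + 14 = 208 days with the visit windows. A constructed subject (assumed values, in multiples of ULN, with normal values before dosing) shows the effect:

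| Day | Type | ALT | Bilirubin |
|---|---|---|---|
| 180 | scheduled | 0.8 | 0.7 |
| 240 | unscheduled | 5.0 | 2.6 |
| 243 | unscheduled | 4.2 | 2.6 |
| 360 | scheduled | 0.9 | 0.8 |

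Under the literal first sentence this subject counts 0 for TEAV, Section 10 ALT, Section 10 bilirubin and DILI. Under the second paragraph the subject counts 1 for each.

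**3. How easily does a scheduled draw miss an episode?** Assume an abnormality lasts D days, with onset uniform over a 180-day interval. The chance that a scheduled draw falls inside it is D/180. For assumed durations of 7, 30 and 90 days this gives 7/180 = 3.9%, 30/180 = 16.7% and 90/180 = 50%. How many such episodes occur, and how many are sampled off schedule, is not known.

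**4. The protocol's own liver repeat tests.** Protocol 7.1.5.2 asks for a repeat within 48 to 72 hours. The trigger is AST or ALT at least 3 x ULN together with total bilirubin at least 2 x ULN, without hemolysis, cholestasis or Gilbert's syndrome. If the transaminase was raised at baseline, it must also be at least 2 times baseline. Suppose a scheduled draw meets the trigger:

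- **DILI:** SAP 5.3.4 uses the same multiples, so the subject is already counted.
- **TEAV:** bilirubin and the triggering transaminase are already abnormal, so their status is set by that draw.
- **Section 10 AST/ALT (above 3 x ULN):** the triggering transaminase is already flagged, unless it is exactly 3 x ULN.
- **Section 10 bilirubin (above 2.5 x ULN):** a subject at 2 to 2.5 on the scheduled draw and above 2.5 only on the repeat is in the count under one rule and out under the other.

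So among the measures that triggered the repeat, only the bilirubin row can change, apart from the exact boundary. Another analyte that first crosses its limit on the repeat falls under step 2.

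**5. Weight of one subject.** TTP488-301 planned 800 patients (SAP 1.6), allocated 1:1 (SAP 1.4): 800/2 = 400 per group as a ceiling. With the denominator fixed, one omitted subject lowers a group proportion by at least 1/400 = 0.25 percentage points. Assumed groups of 200 and 100 give 1/200 = 0.5 and 1/100 = 1.0 points.

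**The case against.** The strongest reply is that the intent is plain. The list in the second paragraph is open-ended, and a subject who ever exceeds an upper limit is one whose maximum exceeds it. The multiple-value rule is tied to a single visit. The count definitions carry no visit limit. All of this stands as evidence of intent. It does not settle the matter, because the first sentence has no qualifier and the SAP never classes ever-met-criterion counts as longitudinal.

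Two further points stand and narrow the concern. SAP 4.2.4 keeps routinely collected laboratory data that the protocol does not require out of the database, so those values reach neither rule. The liver repeats are specified by the protocol and are not in that class. Detection is also protected: Protocol 7.1.5.2 has potential DILI reported as serious adverse events, SAP 5.3.3 has potentially clinically significant laboratory abnormalities reported as TEAEs, and SAP 4.2 has listings medically reviewed.

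A reader might infer three stronger points that the documents do not support:

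- **Safety cases would be lost.** The safeguards just listed do not depend on the table counts.
- **The liver repeat pathway puts the DILI count at risk.** When the scheduled draw met the trigger, DILI status is already set.
- **Proportions could move either way through the denominator,** since SAP 5 reports the number of subjects available for analysis. SAP 3 assigns all safety analyses to the safety set of dosed subjects, and laboratory tests are scheduled at early termination, so this argument is speculative.

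**Conclusion.** The contradiction within SAP 6.5 is real and should be removed, but its consequence is modest. It concerns the reproducibility of tabulated laboratory and vital-sign counts in a descriptive study to which SAP 5.1 allocates no alpha. If the first sentence is followed literally, numerators for TEAV, Section 10 and DILI can be too low wherever the only qualifying value is off schedule. The number of such subjects cannot be derived from the documents. Only the weight of each one can be bounded, and that bound rests on the planned TTP488-301 enrolment as a ceiling and a fixed safety-set denominator. Actual TTP488-303 enrolment is not given. The ECG rows of Section 10 are outside the conflict, because the first sentence names only laboratory data and vital signs.

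**What to change.** In SAP 6.5:

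1. Limit both the exclusion from summaries and the rule for several values at one visit to by-visit summaries.
2. Add: *Subject-level TEAV, Section 10 laboratory and vital-sign, and DILI (5.3.4) counts use all on-treatment post-dose values in the database, scheduled or unscheduled, with on-treatment as defined in 6.2.* That existing definition runs to 45 days after the final administration, so no new cut-off is created.
3. State that laboratory values kept out of the database by 4.2.4 are not reached by this rule.

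The cost is a short edit and a small programming change, and reported numerators may rise. SAP 5.3.4 does not say how close in time an accompanying bilirubin value must be. Admitting repeat liver tests brings more pairs of values into play, and this edit leaves that existing gap as it is.
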